6.2.3.1 Implementation of Dose Escalation Decisions

To implement dose escalation decisions, the available toxicity information (including all safety data, AEs Grade ≥ 2 and laboratory abnormalities that are not DLTs), the assessment of those doses satisfying the EWOC criterion from the BLRM, and the available PK and PD information will all be evaluated by the Investigators and Novartis study personnel (including the study physician and statistician) during a dose decision meeting by teleconference. All occurrences of DLT will be discussed and agreed at the dose decision teleconference among participating investigators and Novartis study personnel.

Cohort enrollment and drug administration at the next higher dose level may not proceed until the investigator receives written confirmation from Novartis indicating that the results of the previous dose level were evaluated and that it is permissible to proceed to a higher dose level with written confirmation of the next higher dose level to be tested.

6.2.3.2 Intra-Patient dose escalation

Intra-patient dose escalation is not permitted at any time within the first 6 months of treatment. After the 6 months of treatment is completed, individual patients may be considered for treatment at doses of MCS110 and PDR001 in combination higher than the doses to which they were initially assigned. Only one of the study drugs will be escalated at any one time. Study drugs will be escalated as detailed in [Section 6.2.2](#). In order for a patient to be treated at a higher treatment dose, he or she must have tolerated the lower dose of MCS110 and PDR001 combination for at least two cycles of therapy (e.g., he or she must not have experienced a toxicity of CTCAE Grade ≥ 2 at the lower dose pair for which relationship to study drug cannot be ruled out). Moreover, the new, higher dose pair with which the patient is to be treated must be a dose pair that has completed evaluation in a dose-escalation meeting and that has satisfied the EWOC criterion under the Bayesian model.

There is no limit to the number of times a patient may have his or her treatment dose increased. Any further increases after the initial intra-patient dose escalation are subject to the same rules as for the initial intra-patient escalation. Consultation with Novartis must occur prior to any

intra-patient dose escalation occurring. These changes must be recorded on the Dosage Administration Record CRF.

6.2.4 Definitions of dose limiting toxicities (DLTs)

A dose-limiting toxicity (DLT) is defined as an adverse event or abnormal laboratory value of CTCAE Grade ≥ 3 assessed as unrelated to disease, disease progression, inter-current illness, or concomitant medications that occurs within the first two cycles of treatment with the combination treatment and meets any of the criteria included in [Table 6-3](#).

Emerging data from the new field of immune-immune combination studies suggest that some immune-related adverse events have a prolonged latency ([Wolchok 2013](#)). As such, the DLT window for the combination cohort in this trial is extended to the length of two cycles or 42 days.

National Cancer Institute Common Terminology Criteria for Adverse events (NCI CTCAE) version 4.03 will be used for all grading. For the purpose of dose-escalation decisions, DLTs will be considered and included in the BLRM.

The investigator must notify the Sponsor immediately of any unexpected CTCAE Grade ≥ 3 adverse events or laboratory abnormalities. Prior to enrolling patients into a higher dose level, CTCAE Grade ≥ 2 adverse events will be reviewed for all patients at the current dose level.

DLTs include any adverse event of CTCAE Grade 3 or higher occurring in the first two cycles of treatment during the Phase Ib dose escalation part of the study, for which relationship to study treatment cannot be ruled, with the exceptions defined in [Table 6-3](#).

Table 6-3 Criteria for defining dose-limiting toxicities

For the purpose of dose escalation and cohort expansion, DLT will be defined as follows: Any Grade 4 AEs will be considered DLTs with the exception of:
Neutropenia lasting ≤ 5 days that is not associated with fever or other clinical symptoms.
Lymphopenia or leukopenia at any grade
Any Grade 3 AEs will be considered DLTs with the exception of:
Electrolyte abnormalities that are not associated with clinical sequelae and are corrected to \leq Gr1 with appropriate management or supplementation within 72 hours of onset.
Infusion reaction that resolves to \leq Grade 1 within 6 hours.
Nausea and vomiting persisting for < 2 days with optimal anti-emetic therapy.
Thrombocytopenia without significant bleeding.
Diarrhea persisting for < 2 days with optimal anti-diarrhea therapy.
Hypertension persisting < 7 days with optimal therapy.
Infection or fever in the absence of neutropenia persisting < 7 days.
Rash or photosensitivity persisting < 7 days after treatment.
Fatigue lasting < 7 days.
Immune-related adverse events persisting at Grade3 < 7 days after treatment with corticosteroids.
*CK elevation without associated muscle damage per investigator discretion
*Isolated AST elevations (without bilirubin or ALT elevations \geq Grade 1)
The following Grade 2 AEs will be considered as DLTs:
Total bilirubin $> 2 \times$ ULN with \geq CTCAE Grade 2 AST/ALT.

Pneumonitis persisting > 7 days despite treatment with corticosteroids.
Eye pain or reduction of visual acuity that does not respond to topical therapy and does not improve to Grade 1 severity within 2 weeks of the initiation of topical therapy OR requires systemic treatment.
Other clinically significant toxicities, including a single event or multiple occurrences of the same event may be considered as DLT's.
* MCS110 treatment results in CK and AST elevations without any association to muscle damage (Radi 2011). The CK/AST elevations are caused by reduced clearance rate from the circulation due to the diminished numbers of macrophages (Kupffer cells) in the liver (Section 1.2.2.1).

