- Include new guidance on dose modifications for suspected immune-related adverse events. To align with recently published guidelines on the clinical management of suspected immune-related toxicities, and to provide guidance for the management of immune related acute dermatologic adverse events seen in study with PDR001, the dose modification section of the protocol and corresponding table were updated. After the recent occurrence of a case of Stevens Johnson Syndrome in a study with PDR001, the dose modification guidelines for protocols using PDR001 were updated to mandate permanent discontinuation of study treatment for patients who experience SJS or Lyell syndrome/toxic epidermal necrolysis (TEN). This change has already been implemented

as part of an urgent safety measure released on 15 June 2018. This protocol amendment is now formalizing these changes in the table describing the criteria for dose reduction/interruption and re-initiation of treatment for adverse drug reactions.

- The withdrawal of consent language was revised to differentiate sample use after a patient withdraws consent based on the different regulations/laws around the world.

Study status

The CMCS110Z2102 study is ongoing in the phase 2 part with MCS110 at 7.5 mg/kg in combination with PDR001. As of 10 April 2018, 60 patients have received the combination of MCS110 and PDR001 at doses of 1 mg/kg and 100 mg (6 patients), 3 mg/kg and 100 mg (12 patients), 3 mg/kg and 300 mg (12 patients), 5 mg/kg and 300 mg (13 patients), 7.5 mg/kg and 300 mg (6 patients), and 10 mg/kg and 300 mg (11 patients), respectively.

Changes to the protocol

Changes to specific sections of the protocol are shown in the tracked changes version of the protocol using strike through red font for deletions and red underlined for insertions.

Section 2.2: Rationale for study design

- The text was updated to reflect the change of design for PDAC patients participating Phase II.

Section 3: Objectives and endpoints

- Table 3-1 Clinical benefit rate in the pancreatic cancer disease group, added as per Amendment 3 is now clearly indicated in the table. [REDACTED]

Section 4.1: Description of study design

- The description of the design of Phase II was updated.
- Figure 4-1 was updated to reflect the change in study design.

Section 4.2: Timing of interim analysis and design adaptations

- The text was updated to reflect the change in the design of Phase II

Section 5.3: Exclusion criteria

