- Consider early referral to specialists with expertise in the diagnosis and management of immune-related AEs to thoroughly investigate events of uncertain etiology.
- Events not included in the study protocol or the reference guidance documents should be managed per institutional preference.

- If one of the study drugs is discontinued the patient may continue with the remaining study drug, if the investigator considers it to be in the patient's best interest. The dose of the remaining study drug must be agreed by Novartis and the investigator.

Patients who discontinue the study treatment for a study related AE or a study-related abnormal laboratory value must be followed as described in [Section 6.3.2](#).

Table 6-4 Dose modification for drug related toxicities

Toxicity	Dose Adjustment Rules*
Hematology	
Neutropenia (ANC)	
Grade 3 or Grade 4.	Hold study treatment. Upon resolution to \leq Grade 2 or baseline within \leq 7 days, resume study treatment without dose modification, after discussion with the Novartis Medical Monitor
Febrile neutropenia	
Grade 3 or Grade 4	Hold study treatment. Upon resolution of fever and improvement of neutropenia to \leq Grade 2 or baseline, resume study treatment without dose modification, after discussion with the Novartis Medical Monitor.
Thrombocytopenia	
Grade 3	Hold study treatment. Upon resolution to \leq Grade 2 or baseline, resume study treatment without dose modification. For Grade 3 associated with major bleeding, discontinue study treatment.
Grade 4	Discontinue study treatment.
Anemia	
Grade 3 or Grade 4	Hold study treatment. Upon resolution to \leq Grade 2 or baseline within \leq 7 days, resume study treatment without dose modification.
Lymphopenia	
Any grade	Treatment-related lymphopenia does not require study treatment hold or discontinuation.
Gastrointestinal	
Diarrhea/colitis*	
Grade 1	May continue study treatment without dose modification. Manage per institutional standard guidelines which should include anti-diarrheal treatment, consideration of corticosteroid therapy, and hydration.
Grade 2	Hold study treatment. GI consultation. Upon resolution to \leq Grade 1 and tapering of steroid requirement to \leq 10 mg prednisone per day, resume study treatment without dose modification after discussion with the Novartis Medical Monitor.

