8.1 Adverse events

8.1.1 Definitions and reporting

An adverse event is defined as the appearance of (or worsening of any pre-existing) undesirable sign(s), symptom(s), or medical condition(s) that occur after patient's signed informed consent has been obtained.

Abnormal laboratory values or test results occurring after informed consent constitute adverse events only if they induce clinical signs or symptoms, are considered clinically significant, require therapy (e.g., hematologic abnormality that requires transfusion or hematological stem cell support), or require changes in study medication(s).

Adverse events that begin or worsen after informed consent should be recorded in the Adverse Events CRF. Conditions that were already present at the time of informed consent should be recorded in the Medical History page of the patient's CRF. Adverse event monitoring should be continued for 150 days after the last dose of PDR001 or 90 days after the last dose of MCS110 for patients who stopped PDR001 and continued MCS110 alone for more than 60 days).

After initiation of new post-treatment antineoplastic therapy, only AEs suspected to be related to study treatment will be collected in the Adverse Events CRF.

Adverse events (including lab abnormalities that constitute AEs) should be described using a diagnosis whenever possible, rather than individual underlying signs and symptoms. When a clear diagnosis cannot be identified, each sign or symptom should be reported as a separate Adverse Event.

Adverse events will be assessed according to the Common Terminology Criteria for Adverse Events (CTCAE) version 4.03. If CTCAE grading does not exist for an adverse event, the severity of mild, moderate, severe, and life-threatening, corresponding to Grades 1 - 4, will be used. CTCAE Grade 5 (death) will not be used in this study but is collected as a seriousness criteria; rather, information about deaths will be collected through a Death form.

The occurrence of adverse events should be sought by non-directive questioning of the patient (subject) during the screening process after signing informed consent and at each visit during the study. Adverse events also may be detected when they are volunteered by the patient (subject) during the screening process or between visits, or through physical examination, laboratory test, or other assessments. As far as possible, each adverse event should be evaluated to determine:

- The severity grade (CTCAE Grade 1-4)

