8.1.2 Laboratory test abnormalities

8.1.2.1 Definitions and reporting

Laboratory abnormalities that constitute an Adverse event in their own right (are considered clinically significant, induce clinical signs or symptoms, require concomitant therapy or require changes in study treatment), should be recorded on the Adverse Events CRF. Whenever possible, a diagnosis, rather than a symptom should be provided (e.g. anemia instead of low hemoglobin). Laboratory abnormalities that meet the criteria for Adverse Events should be followed until they have returned to normal or an adequate explanation of the abnormality is found. When an abnormal laboratory or test result corresponds to a sign/symptom of an already reported adverse event, it is not necessary to separately record the lab/test result as an additional event.

Laboratory abnormalities, that do not meet the definition of an adverse event, should not be reported as adverse events. A Grade 3 or 4 event (severe) as per CTCAE does not automatically indicate a SAE unless it meets the definition of serious as defined below and/or as per investigator's discretion. A dose hold or medication for the lab abnormality may be required by the protocol in which case the lab abnormality would still, by definition, be an adverse event and must be reported as such.

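### Table 6-3 exempts brief, uncomplicated neutropenia from the DLT definition at Grade 4 but not at Grade 3, so the milder event can count as a DLT when the worse one does not

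*Protocol*

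**What the plan says.** Protocol 6.2.4, Table 6-3 classifies AEs in the first two cycles by grade. Every Grade 4 AE is a DLT apart from two items: "Neutropenia lasting ≤ 5 days that is not associated with fever or other clinical symptoms" and "Lymphopenia or leukopenia at any grade". Grade 3 has its own rule: "Any Grade 3 AEs will be considered DLTs with the exception of" a separate list. That list has no neutropenia item; neutropenia appears there only as a qualifier of the infection-or-fever item. The table's closing line lets other toxicities be added as DLTs. It does not let any be removed.

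Table 6-4 has a single row for Grade 3 and Grade 4 neutropenia: hold, and after recovery resume at an unchanged dose.

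On what counts as an AE, Protocol 8.1.1 says: "Abnormal laboratory values or test results occurring after informed consent constitute adverse events only if they induce clinical signs or symptoms", or if they are clinically significant, need therapy or need a change in study medication. Section 8.1.2.1 adds that a dose hold "may be required by the protocol in which case the lab abnormality would still, by definition, be an adverse event".

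Protocol 6.2.3.1 states: "All occurrences of DLT will be discussed and agreed at the dose decision teleconference among participating investigators and Novartis study personnel". SAP 2.5.2.1.1 fits the model to the dose-determining set and lists DLTs on that set, with incidence by system organ class, preferred term and worst grade.

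**The concern.** The exemption runs the wrong way with severity. Neutropenia of five days or less, without fever or symptoms, is excused at Grade 4 and counted at Grade 3. The adjacent lymphopenia and leukopenia item reaches down to Grade 3 by its own wording; the neutropenia item does not. Table 6-4 manages the two grades alike, so nothing in the documents explains a stricter rule for the lower grade.

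Two things are at stake. DLT incidence in cycles 1 and 2 is a Phase Ib primary variable. DLTs are also the on-study input to the Bayesian logistic regression model (BLRM), which bars any dose with a probability of 25% or more that the DLT rate is at least 33% (the EWOC limit). A DLT counted in error raises both. It can slow escalation, but it cannot conceal toxicity.

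**Working it through.** Doses below are MCS110 mg/kg / PDR001 mg.

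**Does the event qualify?** Not every Grade 3 neutrophil count is an AE under 8.1.1. But on Cycle 2 Day 1 hematology and a dose are both due. Grade 3 neutropenia found then triggers the Table 6-4 hold, and 8.1.2.1 makes a laboratory abnormality with a protocol-required hold an AE. If relation to treatment cannot be ruled out, Table 6-3 makes it a DLT even if it resolves within five days without fever or symptoms.

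**Model (Protocol 10.4.2 and Appendix 3).**
- logit π1 = log α1 + β1 log(d1/5)
- logit π2 = log α2 + β2 log(d2/300)
- odds(π12) = exp(η · d1/5 · d2/300) × odds(1 − (1 − π1)(1 − π2))

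Priors are those of Table 14-13, with η normal, mean 0, SD 2.803. Millions of prior draws were weighted by the binomial likelihood Π π^r (1 − π)^(n − r). P(excess) is the weighted share of draws with π12 ≥ 0.33.

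**Reproduction of the protocol's figures.** The prior at 3/100 is 0.106 (stated 0.104). Table 14-15 scenarios 1, 2, 5, 6, 9 and 10 give 0.097, 0.219, 0.061, 0.091, 0.104 and 0.122 (stated 0.097, 0.219, 0.061, 0.092, 0.104 and 0.125).

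**Numbers treated.** The Amendment 04 study status gives 6 at 1/100, 12 at 3/100, 12 at 3/300, 13 at 5/300, and "7.5 mg/kg and 300 mg (6 patients), and 10 mg/kg and 300 mg (11 patients), respectively". The total is 6 + 12 + 12 + 13 + 6 + 11 = 60.

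**Effect of one DLT on the next step.** Assumed: 6 and 12 DLT-free patients at 1/100 and 3/100, and no other DLTs.

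| Data | Dose tested | P(excess) | Open (< 0.25)? |
|---|---|---|---|
| 0 DLTs in 3 to 6 at 3/300 | 5/300 | 0.067 to 0.043 | yes |
| 1 DLT in 3 to 6 at 3/300 | 5/300 | 0.417 to 0.274 | no |
| 1/7 at 3/300 | 5/300 | 0.242 | yes |
| 1 DLT in 3 to 6 at 5/300, after 0/12 at 3/300 | 7.5/300 | 0.425 to 0.282 | no |
| 1/7 at 5/300, after 0/12 at 3/300 | 7.5/300 | 0.248 | barely |
| 1/7 at 5/300, after 0/9, 0/6 or 0/3 at 3/300 | 7.5/300 | 0.262, 0.279, 0.298 | no |
| 1/8 at 5/300, after 0/3 at 3/300 | 7.5/300 | 0.261 | no (opens at 1/9) |
| 0/13 at 5/300, after 0/12 at 3/300 | 10/300 | 0.043 | yes |
| 1/13 at 5/300, after 0/12 at 3/300 | 10/300 | 0.274 | no |
| 1/15 at 5/300, after 0/12 at 3/300 | 10/300 | 0.243 | yes |

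The dose where the DLT occurred stays open throughout: 0.125 to 0.033 at 3/300 and 0.104 to 0.028 at 5/300, for cohorts of 3 to 6.

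From a first cohort of 3, reaching 5/300 takes 7 − 3 = 4 further DLT-free patients; from a cohort of 6 it takes 7 − 6 = 1. For 10/300, the level after 5/300 in Table 6-2, it takes 15 − 3 = 12 or 15 − 6 = 9. The intermediate 7.5/300 is open by 1/13 (0.127).

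**RP2D (7.5/300) at the recorded 60.** With no DLTs, P(excess) is below 0.0001. With one DLT at each of 3/100, 3/300, 5/300, 7.5/300 and 10/300, it is 0.0005 (10/300: 0.022). Three at 7.5/300 and six at 10/300 give 0.238. Two, two, three and four at 3/300, 5/300, 7.5/300 and 10/300 give 0.302.

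**Reported incidence.** One such event adds 1/6 = 16.7 points at 7.5/300, 1/11 = 9.1 at 10/300, 1/13 = 7.7 at 5/300, and 1/12 = 8.3 at 3/100 or 3/300.

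**The case against.** The best case on the other side accepts the asymmetry and disputes its consequence.

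- **Little practical exposure.** The documents do not name neutropenia among the observed or expected toxicities of either drug. The only DLT count they give is none in the first 17 patients. The figures above are what any single DLT would do. All of this stands, and it keeps the point minor.
- **Already visible.** DLTs are listed with incidence by preferred term and worst grade, and Grade 3–4 AEs and neutrophil shift tables are planned. This stands in part: a Grade 3 neutropenia DLT would be seen, but not whether it was brief and uncomplicated, nor what the incidence would be without it.
- **Human review.** DLTs were agreed by teleconference, and dose decisions also used other safety, PK and PD data. This limits the effect. But no text lets the teleconference set aside an event that meets Table 6-3.
- **Phase Ib is closed.** Escalation reached 10/300, the top level of Table 6-2, so no planned dose was lost. This stands.

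A reader might infer that a miscounted neutropenia held the RP2D at 7.5 rather than 10 mg/kg, or that reported DLT rates are inflated. The documents support neither: they show no affected event and do not give the final DLT counts. A reader might equally infer that the cost is at most one extra cohort at an early step. The 10/300 results do not support that.

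**Conclusion.** The rule is wrong as written, and nothing elsewhere in the documents cures it. Severity is minor.

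The error can only add DLTs. One such event can bar the next dose, at later as well as early steps. The wait is until about 1/7 for 5/300, about 1/7 to 1/9 for 7.5/300 depending on how many patients were treated at 3/300 first, and about 1/15 for 10/300. The 0.248 at 1/7 for 7.5/300 lies within the model's reproduction error (up to 0.003) of the limit and should be read as borderline.

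The RP2D stays far inside EWOC under the tested pattern of one DLT per level from 3/100 to 10/300. That is conditional, because treated numbers stand in for evaluable numbers and the final DLT counts are not documented. In the patterns tried, P(excess) came near 0.25 only with about nine or more DLTs, mostly at the top doses. Removing a wrongly counted DLT would move the RP2D further inside the limit. The step results also assume no other DLTs and lower levels filled as stated, since the enrolment order is not given.

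**What to change.** Reword the exemption in Table 6-3 to: *Grade 3 or Grade 4 neutropenia lasting ≤ 5 days without fever or other clinical symptoms*. This also keeps the inversion out of any later protocol that reuses the table.

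As Phase Ib is complete, keep the primary DLT listing as agreed at the teleconferences. In the SAP's DLT section or the CSR, flag any DLT that rests only on brief, uncomplicated Grade 3 neutropenia. Only if there is one, report DLT incidence and the BLRM without it as a supportive check.

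The cost is one line of text, one check of the recorded Phase Ib DLTs for a single category and, at most, one extra model run. No primary result is overwritten.

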6.3 Dose modifications

6.3.1 Dose modification and dose delay

For patients who do not tolerate the protocol-specified dosing schedule, dose adjustments are permitted in order to allow the patient to continue the study treatment, except during the first two cycles when dose modifications are only allowed if the patient experiences a DLT. The following guidelines need to be applied:

- If a patient experiences an AE meeting the criteria for DLT as outlined in Section 6.2.4, treatment should be withheld. Dose modifications for toxicities related to the study medication are summarized in Table 6-4. Following resolution of the toxicity to Grade 1 or to the patient's baseline value, the patient may resume study treatment at a lower dose level than is being tested at that time (on the same dosing schedule), if there is no evidence of disease progression as per irRC. A decision to resume treatment following the occurrence of a DLT is at the discretion of the Investigator. Following an AE meeting criteria for DLT, if a patient resumes study treatment, it should be at the next lower dose level. Dose reductions to doses below MCS110 0.3mg/kg / PDR001 100 mg Q3W are not permitted. If more than 2 consecutive doses have to be skipped due to study treatment-related toxicities, then the patient must be discontinued from the study unless the patient experiences clinical benefit in the opinion of the investigator. In this case, treatment can be continued at a dose agreed by Novartis and the investigator.
- For clinical management of suspected immune-related events, reference to consensus management guidelines is recommended such as those provided in the National Comprehensive Cancer Network (NCCN) Guidelines for the Management of Immunotherapy-Related Toxicities (available at : https://www.nccn.org/professionals/physician_gls/default.aspx#immunotherapy), the American Society for Clinical Oncology clinical practice guideline for Management of Immune-Related Adverse Events in Patients Treated With Immune Checkpoint Inhibitor Therapy (Brahmer 2018) or the European Society for Medical Oncology (ESMO) Clinical Practice Guidelines for Management of Toxicities from Immunotherapy (Haanen 2017). Note that in general, study treatment should be interrupted for grade 3 and 4 toxicities and for a subset of lower grade toxicities.
- Consider early referral to specialists with expertise in the diagnosis and management of immune-related AEs to thoroughly investigate events of uncertain etiology.
- Events not included in the study protocol or the reference guidance documents should be managed per institutional preference.

- If one of the study drugs is discontinued the patient may continue with the remaining study drug, if the investigator considers it to be in the patient's best interest. The dose of the remaining study drug must be agreed by Novartis and the investigator.

Patients who discontinue the study treatment for a study related AE or a study-related abnormal laboratory value must be followed as described in [Section 6.3.2](#).

Table 6-4 Dose modification for drug related toxicities

Toxicity	Dose Adjustment Rules*
Hematology	
Neutropenia (ANC)	
Grade 3 or Grade 4.	Hold study treatment. Upon resolution to \leq Grade 2 or baseline within \leq 7 days, resume study treatment without dose modification, after discussion with the Novartis Medical Monitor
Febrile neutropenia	
Grade 3 or Grade 4	Hold study treatment. Upon resolution of fever and improvement of neutropenia to \leq Grade 2 or baseline, resume study treatment without dose modification, after discussion with the Novartis Medical Monitor.
Thrombocytopenia	
Grade 3	Hold study treatment. Upon resolution to \leq Grade 2 or baseline, resume study treatment without dose modification. For Grade 3 associated with major bleeding, discontinue study treatment.
Grade 4	Discontinue study treatment.
Anemia	
Grade 3 or Grade 4	Hold study treatment. Upon resolution to \leq Grade 2 or baseline within \leq 7 days, resume study treatment without dose modification.
Lymphopenia	
Any grade	Treatment-related lymphopenia does not require study treatment hold or discontinuation.
Gastrointestinal	
Diarrhea/colitis*	
Grade 1	May continue study treatment without dose modification. Manage per institutional standard guidelines which should include anti-diarrheal treatment, consideration of corticosteroid therapy, and hydration.
Grade 2	Hold study treatment. GI consultation. Upon resolution to \leq Grade 1 and tapering of steroid requirement to \leq 10 mg prednisone per day, resume study treatment without dose modification after discussion with the Novartis Medical Monitor.
Grade 3	Hold study treatment. GI consultation. Upon resolution to \leq Grade 1 and tapering of steroid requirement to \leq 10 mg prednisone per day, consider resuming study treatment after discussion with the Novartis Medical Monitor.
Grade 4	Discontinue study treatment.

Toxicity	Dose Adjustment Rules*
Hepatic (AST and/or ALT elevation)	
Grade 2 AST and/or ALT	Hold study treatment. Manage per institutional practice. Upon resolution to \leq Grade 1 or baseline, consider resuming study treatment without dose modification.
Grade 2 transaminitis with bilirubin $>1.5 \times$ ULN (unless Gilbert's syndrome)	Discontinue study treatment.
Grade 3 AST and/or ALT	Hold study treatment. Manage per institutional practices. Upon resolution to \leq Grade 1 or baseline within 7 days, consider resuming study treatment without dose modification after discussion with the Novartis Medical Monitor. Otherwise, discontinue study treatment
Grade 4 AST and/or ALT	Discontinue study treatment.
Isolated total bilirubin elevation**	
Grade 2	Hold study treatment. Upon resolution to \leq Grade 1 or baseline, may continue study treatment without dose modification.
Grade 3	Hold study treatment. Upon resolution to \leq Grade 1 or baseline, may consider resuming study treatment after discussion with the Novartis Medical Monitor.
Grade 4	See footnote**. Otherwise, discontinue study treatment.
Asymptomatic amylase and/or lipase elevation***	
Grade 3 or Grade 4, not associated with symptoms or clinical manifestations of pancreatitis***	Continue study treatment. If levels do not resolve to \leq Grade 2 within \leq 14 days after the initial report, hold study treatment. Upon resolution to \leq Grade 2, may resume study treatment without dose modification, after discussion with the Novartis Medical Monitor.
Pancreatitis	
Grade 2 / radiologic evidence	Hold study treatment. Manage per institutional practice. Upon resolution to \leq Grade 1, may resume study treatment without dose modification, if no clinical evidence of pancreatitis and after discussion with the Novartis Medical Monitor.
Grade 3-4	Discontinue from treatment.
CK elevation	
Grade 3-4	Monitor CK-MB isoenzyme, troponin (I or T), and creatinine. 
 • If CK-MB and troponin (I or T) are normal, creatinine $\leq 1.5 \times$ baseline and patient asymptomatic, continue treatment. • If CK-MB and troponin (I or T) are abnormal or creatinine ($> 1.5 \times$ baseline and $> \text{ULN}$) or patient symptomatic, delay treatment and explore alternative causes for elevated CK (for example myositis and rhabdomyolysis) according to local guidelines. 
After recovery of CK-MB, troponin (I or T) and creatinine to Grade 1 or baseline, restart treatment. Decrease MCS110 1 dose level.

Cytokine Release Syndrome (CRS)	
Grade 2	See instructions for Grade 2 Infusion Reaction.

Toxicity	Dose Adjustment Rules*
Grade 3 and Grade 4	Discontinue study treatment. Follow-up CRS as per institutional guidelines. Take blood for cytokine measurements as specified in Section 7.2.2.5.5 Laboratory evaluations.
Renal (creatinine)	
Grade 2	Hold study treatment. Consider resuming study treatment without dose modification upon resolution to \leq Grade 1 with appropriate management..
Grade 3 or 4	Discontinue study treatment.
Endocrine	
Hypothyroidism or hyperthyroidism	
Grade 2	May continue study treatment without dose modification. Management according to institutional practice.
Grade 3	Hold study treatment. Upon resolution to Grade \leq 1 with appropriate management, may resume study treatment without dose modification.
Grade 4	May resume therapy following resolution or control with physiologic hormone replacement.
Other endocrine disorders	
Grade 2 and Grade 3	Hold study treatment. Upon resolution to Grade \leq 1 with appropriate management, may resume study treatment without dose modification.
Grade 4	Hold study treatment. Grade 4 treatment-related endocrinopathies, such as adrenal insufficiency, adrenocorticotrophic hormone (ACTH) deficiency, hyper- or hypothyroidism, or glucose intolerance, which resolve or are adequately controlled with physiologic hormone replacement (corticosteroids, thyroid hormones) or glucose-controlling agents, respectively, may not require discontinuation after discussion with and approval from the Novartis Medical Monitor.
Pulmonary (pneumonitis)	
Grade 1	Consider study treatment hold. Manage per institutional practice. Consider resuming study treatment upon radiographic evidence of improvement.
Grade 2	Hold study treatment. Pulmonary and infection workup. Upon resolution to \leq Grade 1, may resume study treatment without dose modification
Grade 3 or 4	Discontinue study treatment.
Ocular (uveitis)	
Grade 1	Continue study treatment without dose modification. Ophthalmology consultation.
Grade 2	Hold study treatment. Urgent ophthalmology consultation. Upon resolution to \leq Grade 1 may consider resuming study treatment without dose reduction after discussion with the Novartis Medical Monitor and in consultation with ophthalmology

Toxicity	Dose Adjustment Rules*
Grade 3 or 4	Discontinue from treatment. Urgent ophthalmology consultation.
Periorbital edema	
Grade 2	Delay treatment until resolved to ≤ Grade 1. Decrease MCS110 1 dose level.
Grade 3-4	Discontinue from treatment.
Dermatology (rash)	
Grade 1	Continue study treatment without dose modification. Topical steroids, antihistamines, topical emollients
Grade 2	Consider holding study treatment. Topical or oral steroids, antihistamines. If study treatment is held and resolution to ≤ Grade 1, resume study treatment without dose modification.
Grade 3 or Grade 4	Hold study treatment. Manage per institutional practice. After resolution to ≤ Grade 1, consider resuming study treatment after discussion with the Novartis Medical Monitor.
Bullous dermatitis	Hold study treatment. Grade 1-2 bullous dermatitis: discussion with the Novartis Medical Monitor is required before considering resuming study treatment. Grade 3 bullous dermatitis: consider resuming therapy after expert consultation and documented discussion with the Novartis medical monitor. Grade 4 bullous dermatitis: discontinue study treatment.
Stevens-Johnson syndrome (SJS), or Lyell syndrome/toxic epidermal necrolysis (TEN)	Permanently discontinue study treatment.
Cardiovascular	
ECG QTc-Interval prolonged; hypertension	
Grade 3	Hold study treatment. Upon resolution to Grade ≤ 1 or baseline (hypertension, QTc) or < 30 msec difference from baseline (QTc) within ≤ 7 days, may resume study treatment without dose modification after discussion with the Novartis Medical Monitor. Baseline ECG refers to the ECG(s) collected at screening
Grade 4	Discontinue study treatment
Other cardiovascular disorders	
Grade 2 (except myocarditis)	Hold study treatment. Upon resolution to Grade ≤ 1 or baseline, may resume study treatment without dose modification after discussion with the Novartis Medical Monitor..
Grade 2 myocarditis, or Grade ≥ 3 other cardiac disorders related to study treatment	Discontinue study treatment
Musculoskeletal	
Grade 2 or Grade 3	Hold study treatment. Consider resuming study treatment without dose modification upon resolution to ≤ Grade 1 with appropriate management.
Grade 4	Discontinue study treatment. In some cases, resuming study treatment may be considered after discussion with the Novartis Medical Monitor and consultation with a rheumatologist.

Toxicity	Dose Adjustment Rules*
Neurology	
Grade 1	Consider study treatment hold, particularly for clinical suspicion of Guillain-Barre syndrome, encephalitis, aseptic meningitis, transverse myelitis, or peripheral neuropathy.
Grade 2	Hold study treatment. In some cases, resuming study treatment may be considered after discussion with the Novartis Medical Monitor.
Grade 3 or Grade 4	Discontinue study treatment.
Infusion Reaction	
Grade 1	Decrease infusion rate until recovery
Grade 2	Stop infusion. Before restarting - administer oral pre-medication (e.g. 1000 mg of acetaminophen/paracetamol, 50-100 mg diphenhydramine hydrochloride or alternative antihistamine), within 60 minutes of restarting the infusion. Restart infusion at 50% of previous rate under continuous observation. Ensure that there is a minimum observation period of 1 hour prior to restarting the infusion(s). If the AE recurs at the reinitiated slow rate of infusion, and despite oral pre-medication, then discontinue patient from treatment.
Grade 3 or 4	Discontinue infusion immediately, and discontinue study treatment. Provide supplemental oxygen, fluids, and other resuscitative measures as needed. Monitor vital signs (e.g. blood pressure, pulse, respiration, and temperature) every 15 ± 5 minutes until resolution.
Other laboratory adverse events, not specified elsewhere in table and not included in the consensus guidelines	
Grade 3	Hold study treatment. Upon resolution to ≤ Grade 1, resume study treatment without dose modification.
Grade 4	Isolated Grade 4 electrolyte abnormalities not associated with clinical sequelae and corrected after appropriate management within 72 hours of their onset do not require discontinuation. In the case of Grade 4 electrolyte imbalances associated with clinical sequelae, or not resolved to ≤ Grade 1 within 72 hours despite appropriate management, discontinue study treatment.
Other non-laboratory adverse events, not specified elsewhere in table and not included in the consensus guidelines	
Grade 2	Consider study treatment hold, at Investigator discretion. Upon resolution to ≤ Grade 1, resume study treatment without dose modification.
Grade 3	Hold study treatment. Upon resolution to ≤ Grade 1, resuming study treatment must be discussed with the Novartis Medical Monitor.
Grade 4	Discontinue from treatment.
*Delay: treatment may be delayed for 7 days due to AEs. If a scheduled dose of ongoing study drugs is delayed longer than 7 days due to an unresolved AE, the administration should be skipped and treatment resumed at a lower dose level (if meeting the criteria for DLT) at the next scheduled dose (Section 6.1.1). Treatment: refers to both study drugs, unless one has been discontinued.	

Toxicity	Dose Adjustment Rules*
**Note: If Grade 3 or 4 hyper-bilirubinemia is due to the indirect (non-conjugated) component only, and hemolysis as the etiology has been ruled out as per institutional guidelines (e.g., review of peripheral blood smear and haptoglobin determination), then delay study treatment until resolved \leq Grade 1, and resume study treatment at the discretion of the investigator.	
***Note: A CT scan or other imaging study to assess the pancreas, liver, and gallbladder must be performed within one week of the first occurrence of any \geq Grade 3 of amylase and/or lipase.	

